### A. **Data Management: Amazon Cloud**

Using 128 bit RSA Secure Socket Layer (SSL) encryption, approved users will be logged-in to machines using secured browsers behind the Partners Healthcare Systems IS corporate firewall or the RIH firewall. Staff will have a unique identifying key that will link them to the electronic study forms. This unique ID will be used in addition to a randomly generated secure password that only the staff person will have. Additional confidentiality procedures are detailed in the Human Subjects section.

### B. **Statistical Analyses Plan for Research Aims**

Each of the statistical tests below will use a two-tailed alpha-level of 0.05.

**Aim 1: Hypothesis 1a and 1b:** *CBT will be superior to MBCT in increasing daily steps over the course of 8-weeks of treatment and after 8 additional weeks of follow-up, and both forms of treatment will be superior to the Fitbit-only, control group.* The primary hypothesis, or Hypothesis 1a, is that the CBT group will do better than the MBCT group at increasing the number of daily steps. A secondary hypothesis, or Hypothesis 1b, is that the CBT and MBCT groups will do better at increasing the number of steps as measured by the FitBit over the 16-week study compared to the FitBit-only group. Since the data for Hypotheses 1a and 1b both use repeated measures on subjects, we will conduct analyses for both hypothesis using general linear mixed models that account for the covariance of observations within subjects. For both hypotheses, we will model a random intercept and slope for subjects and site and fixed effects for treatment, time, and potentially confounding covariates. The treatment by time interaction for both hypotheses will be used to assert the statistical significance of treatment effects. Canonical links will be used to correctly model the distribution of dependent variables: for count data (e.g. steps) Poisson regression

models will be fit with the Poisson family and the log link and for normally distributed data linear regression models will be fit with the Gaussian distribution and identity link. To choose the correct model for the hypotheses, we will use the Shapiro-Wilk test to assess for normality as well as the deviance statistic, the Akaike information criterion and the Bayesian information criterion to assess the best fitting model. We will compare nested models with the likelihood ratio chi-square statistics for both hypotheses. When a treatment effect is significant for either Hypothesis 1a or 1b, we will clarify its clinical significance by computing, for each time point, effect size statistics that convey the magnitude of treatment group differences. For effect size of both hypotheses, we will use the standardized mean difference for continuous variables. Our primary analyses for Hypotheses 1a and 1b will use daily steps as measured by Fitbit (primary outcome), and then self-reported physical activity, weight, perceived stress, PHQ-9, Altman Mania Scale Scores, and Sheehan disability scores as secondary outcome measures

**Aim 2: Exploratory Aims (Phase II).** *Hypotheses:* Between treatment group effects sizes (and 95% CI) will be calculated. To supplement this, Mann-Whitney tests will compare treatment groups on medical burden (as measured by FRS) (*Hypothesis 2a*) and on improvement in symptoms (PHQ-9, ASRM) and functioning (SDS) (*Hypothesis 2b*) based on change from baseline.

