**III. INTERVENTION MODULES AND OVERVIEW**

Participants in both therapy-based interventions will access materials (e.g., client vignettes, videos, activities) that illustrate ways to increase physical activity (e.g., walks, runs, climbing stairs, etc.). They will be guided to gradually increase their daily steps (physical activity) at their own pace. Both CBT and MBCT will be provided online and will guide participants through the elements of each treatment which are geared to address the barriers against exercise that individuals with mood disorders at risk for or with CVD face (fear of the physiological signs of exertion as they may mean a heart attack, etc.). Besides structured guidance towards exercise, the main focus of both treatments will be on addressing these obstacles that prevent individuals from engaging in exercise. Participants in both of these groups will receive Fitbit devices to measure their steps (main outcome) throughout the study. In addition to the two treatment-based intervention group there will also be a group of participants who serve as controls. This group will receive a Fitbit device, but no form of therapy and will not have access to the online therapy material. By including this control group, we will be able to ensure that any treatment effect is not due to wearing a Fitbit.

**Cognitive-behavioral therapy (CBT):** CBT will be based on previous work using CBT to enhance exercise in individuals with mood disorders which includes the following elements: (1) identifying and setting realistic exercise-based goals and intermediate goals (to maximize success to increase motivation); (2) behavioral scheduling to optimize when to exercise, identify rewards for exercising, and problem solve obstacles to exercising; and (3) identify dysfunctional, maladaptive thoughts about exercise (which decrease motivation) and skills to identify more adaptive, positive thoughts (to overcome thoughts of being too tired or too stressed to exercise). These aspects follow the core components of CBT, or to change dysfunctional thoughts and behaviors to change a problem behavior (i.e., sedentary behavior). Evidence shows that adjunctive CBT for exercise helps patients improve their planning to exercise, motivation to exercise, and self-efficacy (or one's belief in their ability) to exercise. Two hundred participants will be randomized to this group.

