**Fitbit-Only Control Group:**

Participants assigned to the Fitbit-only control study group you will not be receiving therapy. However, they will receive a Fitbit, which they will be asked to wear over the course of 16 weeks as well as to complete the same schedule of assessments as the therapy arms. One hundred participants will be randomized into this group.

Participation in this study can be added to an individual's regular course of treatment (such as medications) but should not replace ongoing treatment with his/her own doctor. Throughout participation in this study, the participant should continue any medications or treatments that his/her own doctor feels will best treat the symptoms of depression and/or cardiovascular disease.

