#### **IV. RESEARCH DESIGN AND METHODS**

##### **Overview**

Given that majority of participants screened will not be eligible, we plan to screen 5000 individuals with the expectation that 10% will be eligible. We propose to recruit 500 eligible

patients from the ongoing MoodNetwork and the Health eHeart Alliance studies who self-report a history of depression and are at elevated risk for cardiovascular events. 40% of participants (2000) will be recruited from MoodNetwork, while 60% (3000) will be recruited from Health-eHeart. Participation will take a total of 16 weeks. During the first 8 weeks, participants will receive online CBT and a fitbit device to track activity, online MBCT and a fitbit device to track activity, or a fitbit device to track activity but no adjunctive therapy. The second 8 weeks are a follow-up period where participants will be asked to continue wearing their fitbit device, but receive no other form of treatment, regardless of which group they were initially randomized to. Participants will use desktop computers, laptops, tablet devices, or phones to participate in this study. These procedures are described in detail below.

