Accessed through a links managed by MoodNetwork.org and Health-eHeart.org, interested participants will sign an online consent form waiver, found in a web portal hosted by the Eureka mHealth Research Platform. Eureka is a multi-tenant system (architecture in which a single instance of a software application serves multiple customers), which is housed on a HIPAA compliant Amazon cloud database. Once the participant has read and electronically signed the waiver of consent form, participants will register for Eureka and then complete a short battery of assessments to determine eligibility. The assessments will consist of 3 standard psychological assessments (The Patient Health Questionnaire [PHQ-9], the Altman Self-Rating Mania Scale [ASRM], and the Mini International Neuropsychiatric Interview [MINI], and 2 cardiac health assessments (The Duke Activity Status Index [DASI], and the International Physical Activity Questionnaire [IPAQ]). They will also be asked to complete a standard demographic form, and their medical and psychiatric histories. If they are not eligible, they will be thanked for their interest and informed that unfortunately, they are not eligible. If found eligible, they will provide their mailing address information so that we can ship them a Fitbit device. Once they receive their Fitbit device, they will return to the study portal to sync their fitbit with our system so that we can collect their step data complete a series of questionnaires, including the World Health Organization Composite International Diagnostic Interview for Bipolar Spectrum Disorders (CIDI), The Patient Health Questionnaire (PHQ-9), The Altman Self-Rating Mania Scale (ASRM), The Sheehan Disability Scale (SDS), The World Health Organization-5 Well-Being Index (WHO-5), the Self Efficacy for Exercise (SEE), the International Physical Activity Questionnaire (IPAQ), the Seattle Angina Questionnaire-7 (SAQ-7) and the Perceived Stress Scale (PSS). Once completed, participants will be randomized to CBT + Fitbit, MBCT + Fitbit, or the Fitbit-only control group. Those who are randomized to one of the two therapy-based treatment groups will be sent to a portal on MoodNetwork.org to access the interventions. Those randomized to the Fitbit-only treatment group will be brought to a page thanking them for their participation, reminding them to wear their fitbit for the next 16 weeks, and informing them that they will be emailed reminders when they need to return to the portal to complete surveys. All participants, regardless of study group, will be asked to return to Eureka in weeks 2, 4, 6, 8, and 16 to complete a battery of assessments and asked questions about adverse events that may have occurred since beginning the study (detailed in Table 1 below).

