### **Participant Selection and Recruitment**

Participants (N = 5000) will be recruited from MoodNetwork.org and health-ehartstudy.org. Participation will take 16 weeks and will involve (1) 8 weeks of receiving online CBT and use of a fitbit, MBCT and use of a fitbit, or use of a fitbit with no adjunctive therapy and (2) 8 weeks of follow-up. Participants will use desktop computers, laptops, tablet devices, or phones to participate in this study. An IRB approved electronic alteration of a written Informed Consent will be obtained from all patients before protocol-specified procedures are carried out. Patients will be recruited according to the following criteria:

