#### d. Targeted Enrollment

We expect to recruit a representative sample of the US. We expect that our sample will resemble the general population given the recruitment sites, or MoodNetwork and Health eHeart.

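### The primary model gives site a random intercept and slope, but there are only two recruitment sites; network should be a pre-specified fixed effect

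*Combined protocol and SAP*

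**What the plan says.** Section VIII.B, Aim 1, sets one mixed-model structure for the primary Hypothesis 1a and the secondary Hypothesis 1b: "we will model a random intercept and slope for subjects and site and fixed effects for treatment, time, and potentially confounding covariates". Treatment effects are judged by the treatment-by-time interaction, two-sided at 0.05. The same section then chooses between models by the deviance, AIC and BIC, and compares nested models by likelihood-ratio chi-square.

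The analysis section does not define site. Section IV.d speaks of representativeness "given the recruitment sites, or MoodNetwork and Health eHeart". The Overview in section IV gives the split: "40% of participants (2000) will be recruited from MoodNetwork, while 60% (3000) will be recruited from Health-eHeart". Participant Selection and Recruitment names the same two sources: "Participants (N = 5000) will be recruited from MoodNetwork.org and health-ehartstudy.org".

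The plan states no covariance structure for the site effects and no fallback for a singular or non-converged fit. It does not name network as a fixed covariate or as a stratification factor.

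**The concern.** A variance component describes the spread of a population of levels, and two levels say almost nothing about that spread. The plan asks them for two variances and, in the usual specification, a covariance as well. The primary model therefore contains a part that the data cannot estimate, and the plan does not say what happens next. An analyst who meets a singularity warning, or who follows the planned model comparison, may simplify or remove the site terms once the outcome data are in view. Nothing else named in the plan would then adjust for network.

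A second consequence concerns the first part of Aim 1, which asks whether the therapies improve activity. If a within-arm time trend is reported from this model, its standard error includes the site-slope variance, which does not cancel as it does between arms.

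**Working it through.** The plan gives no power, variance or site figure to reproduce here.

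**Inputs from the documents.** Two sites. Planned enrolment of 500: "we plan to screen 5000 individuals with the expectation that 10% will be eligible", and 0.10 × 5000 = 500. CBT and MBCT: "Two hundred participants will be randomized to this group" (200 each). Control: "One hundred participants will be randomized into this group". Attrition 20% (section VIII.C). Individual randomisation (section IV, Overview).

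**Assumptions, not in the documents.** The 40/60 split of those screened carries over to those enrolled (0.4 × 500 = 200 and 0.6 × 500 = 300). Gaussian model on weekly means over 16 weeks; subject SDs 2500 steps (intercept) and 100 steps/week (slope); residual SD 1500; site SDs from 0 and 0 up to 1000 steps and 50 steps/week.

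**1. Rank.** Let d be the difference between the two sites in (intercept, slope), with d ~ N(0, 2G + V), where G is the site covariance and V the sampling covariance. G has three parameters; d is a single vector. With z = V^(-1/2) d, the matrix zz' has one non-zero eigenvalue, |z|². The REML solution puts (|z|² − 1), floored at zero, on that one direction. The estimate of G therefore has rank 0 or 1, never 2, whatever SDs are assumed.

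Hand check with no true site variation: rank 0 has probability P(χ² on 2 df ≤ 1) = 1 − e^(−0.5) = 0.393. If the terms are independent and their sampling errors uncorrelated, at least one zero has probability 1 − 0.3173² = 0.899. The first row below agrees.

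**2. Simulated boundary rates, N = 400.**

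| Site SD (steps; steps/week) | Correlated, rank 2 | Correlated, rank 0 | Independent, at least one zero |
|---|---|---|---|
| 0; 0 | 0% | 40% | 90% |
| 250; 10 | 0% | 18% | 74% |
| 500; 25 | 0% | 6% | 50% |
| 1000; 50 | 0% | 2% | 27% |

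Over N = 320 to 500 the last column runs from 23% to 90%; a separate check gave 33% to 91%. Full REML fits of the correlated structure were singular in 150 of 150 trials.

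**3. One degree of freedom.** The 95% interval for a site variance runs from 1/5.02 = 0.2 to 1/0.00098 = about 1018 times the estimate.

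**4. Effect on the treatment contrast.** In the 150 trials (CBT against MBCT, 200 per arm), the mean standard error of treatment-by-time, in thousands of steps, was 0.1032 with random site, 0.1034 with fixed site and 0.1042 with no site term. Random-site and fixed-site estimates differed by 0.01 SE on average and 0.06 SE at most. In the separate check the figures were 0.01 to 0.02 SE on average and about 0.13 SE at most.

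**5. If the site terms are dropped.** The shift equals the chance imbalance in network share between arms times the network difference in trend, δ. The SD of the imbalance is √(0.4 × 0.6 × (1/200 + 1/200)) = 0.049. The SE of the contrast is s√(2/200) = 0.1s, where s is the SD of individual estimated trends. A typical shift is therefore 0.49 × δ/s standard errors: 0.12 SE at δ = 0.25s and 0.24 SE at δ = 0.5s. Simulation under assumed true network differences gave 0.1 to 0.2 SE on average, with a largest single run of 1.4 SE.

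**6. Within-arm trend.** With 16 weekly means, Σ(t − t̄)² = 340, so s² = 100² + 1500²/340 = 16,618. For an arm of 200 the variance of the mean trend is 16,618/200 = 83 (SE 9.1 steps/week). A site-slope SD of 25 adds about 25²/2 = 312, giving an SE of about 19.9. The added part is estimated on one degree of freedom.

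**The case against.** The strongest reply is that a singular fit is not a failed fit. Software usually still returns the treatment-by-time estimate, and step 4 shows it almost identical to the fixed-site result. That stands, and no non-convergence was shown. A reader might infer that the primary model cannot be fitted or that the primary comparison is biased; the documents support neither. With individual randomisation, omitting network causes no systematic bias in the linear model, only chance-imbalance noise of the size in step 5.

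Singularity is also certain only for correlated terms. Where networks truly differ by 500 steps and 25 steps/week or more, both site components vanish in about 6% of trials or fewer, so some adjustment usually survives if the terms are kept. The clause on potentially confounding covariates could admit network, though it does not name it. Data-driven model choice is a general feature of section VIII.B, not something that the site terms create.

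Site is undefined, so the two-network reading is an inference. The other reading that the text offers, the two institutions sharing data in section VII, also has two levels.

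A reader might also argue that therapy favours MoodNetwork members, because those allocated to it "will be sent to a portal on MoodNetwork.org to access the interventions". The documents do not say so. Everyone registers and completes surveys on Eureka, and such an effect would be a treatment-by-network interaction, which is a different question. Nor do they say that steps are expected to differ by network.

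Finally, the percentages come from a Gaussian model, while the plan names Poisson regression with a log link for steps. The limit of one contrast follows from the number of levels; the rates are illustrative.

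**Conclusion.** The point holds as a specification fault of minor to moderate severity. The certain part needs only two sites and a correlated site covariance. The frequency under independent terms depends on the assumed SDs. If the terms stay in, the numerical effect on the primary contrast is negligible. What remains is an unspecified analytic choice that could be made after seeing the data, typically worth 0.1 to 0.2 SE under assumed network differences and occasionally more, together with poorly determined standard errors for any within-arm trend. The likelihood-ratio comparison does not settle the choice, because its usual chi-square reference does not apply to variances on the boundary.

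**What to change.** In section VIII.B, Aim 1:

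- Define site as recruitment network (MoodNetwork or Health eHeart).
- Keep the random intercept and slope for subjects.
- Replace the random site terms with fixed effects for network and network-by-time.
- State that both fixed terms stay in the model whatever the AIC, BIC, deviance or likelihood-ratio comparisons show.

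The cost is a wording change and two fixed-effect parameters among about 500 participants; the simulations showed no meaningful loss of precision (0.1034 against 0.1032). Conclusions become conditional on these two networks, but two levels could not support wider generalisation anyway. If time is linear, the network-by-time term removes a linear difference in trend, not every possible difference. Stratifying randomisation by network is optional and not needed for this correction.

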### A. Primary Aims

**Aim 1: To determine if 1) web-based CBT or web-based MBCT, supported by use of Fitbit technology for self-tracking of activity, improves physical activity, and 2) How these two therapies compare to a Fitbit-only control group.**

*Hypothesis 1a:* Because CBT (compared to MBCT) is the more directive intervention, we hypothesize that CBT will be superior to MBCT in increasing daily steps over the course of 8-weeks of treatment and at follow-up.

*Hypothesis 1b:* Both forms of therapy-based treatment will be superior to the Fitbit only control group in increasing daily steps over the course of 8-weeks of treatment and at follow-up.

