## VIII. DATA ANALYSIS

Baseline demographic and clinical characteristics will be examined by the PI in collaboration with [name]., Professor of Biostatistics. Measures of central tendency and variability will be estimated on each continuous measure; proportions estimated for categorical variables. Transformations will be used when distributional assumptions are not fulfilled for inferential tests. Dropouts and completers will be compared on baseline variables using Mann-Whitney or chi-square tests. Following FDA guidance for clinical trials, we will not correct our single primary outcome for multiple comparisons. We have 61 additional secondary/exploratory analyses. These will be corrected for multiple comparisons using the Bonferroni method, which yields an alpha level of 0.0008.

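### Hypothesis 1b claims that both therapies beat Fitbit-only, but the plan names no contrasts and no rule that would support a claim about both

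*Combined protocol and SAP*

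**What the plan says.** Section II.A (Primary Aims) states Hypothesis 1b for each therapy: "Both forms of therapy-based treatment will be superior to the Fitbit only control group in increasing daily steps". Section VIII.B repeats it: "both forms of treatment will be superior to the Fitbit-only, control group". The same paragraph then restates it more loosely, "A secondary hypothesis, or Hypothesis 1b, is that the CBT and MBCT groups will do better", which could also describe the two therapies taken together.

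The decision rule, in section VIII.B, is "The treatment by time interaction for both hypotheses will be used to assert the statistical significance of treatment effects". No coding of treatment, degrees of freedom or contrasts are given. The section goes on to say that nested models will be compared by likelihood ratio chi-square for both hypotheses. After a significant result, "we will clarify its clinical significance by computing, for each time point, effect size statistics"; these are standardised mean differences, and no pairwise test is attached to them.

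On alpha, section VIII.B says "Each of the statistical tests below will use a two-tailed alpha-level of 0.05". The opening of section VIII, repeated in VIII.D, says "We have 61 additional secondary/exploratory analyses" and "These will be corrected for multiple comparisons using the Bonferroni method, which yields an alpha level of 0.0008".

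**The concern.** A claim that both therapies are superior is a joint claim, and it needs evidence for each. A treatment-by-time test over three arms rejects when any arm departs from the others, including when CBT and MBCT merely differ from one another. A pooled therapy-versus-control test can reject because one therapy works and carries the average. Under either reading, an inactive therapy could be reported as better than Fitbit-only on the strength of the other.

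Section III adds the control arm so that an effect of therapy can be told apart from an effect of wearing the device, and section I foresees disseminating two interventions. Each therapy therefore needs its own comparison with control. If the contrasts are not fixed beforehand, the choice among them falls after the data are seen.

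**Working it through.** **Inputs.** Randomised 200 CBT, 200 MBCT, 100 Fitbit-only (section III). Attrition 20% (VIII.C), here applied equally to each arm: 200 × 0.8 = 160, 160, and 100 × 0.8 = 80. Alpha 0.05 (VIII.B) or 0.0008 (VIII and VIII.D).

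**The plan's own figure.** 0.05/61 = 0.00082, which rounds to the stated 0.0008. It reproduces.

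**Assumptions.** The plan gives no effect size or SD. I take participant slopes standardised to SD 1, linear time and normal theory. CBT differs from control by d = 0.2 to 0.5, and MBCT by exactly 0. The two therapy arms are the same size, so exchanging them changes nothing.

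**Three-arm test, 2 df.** The non-centrality is the sum over arms of n × (arm mean − overall mean)². The overall mean is 160d/400 = 0.4d, so it equals 160(0.6d)² + 240(0.4d)² = 96d². The critical values are 5.99 at 0.05 and 14.21 at 0.05/61.

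**Pooled test, 1 df.** The expected difference is d/2, with standard error √(1/320 + 1/80) = 0.125, so the expected z is 4d. The critical values are 1.96 and 3.35.

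**Both contrasts required.** Since MBCT is null, a false joint claim cannot be more frequent than a one-directional false positive for MBCT: 0.05/2 = 2.5%, or 0.00082/2 = 0.04%.

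Chance of a significant result when only CBT works:

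| d | 2-df, 0.05 | 2-df, 0.05/61 | Pooled, 0.05 | Pooled, 0.05/61 |
|---|---|---|---|---|
| 0.2 | 40% | 5% | 12% | 0.5% |
| 0.3 | 75% | 25% | 22% | 1.6% |
| 0.4 | 95% | 61% | 36% | 4% |
| 0.5 | 99.5% | 89% | 52% | 9% |

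With no attrition (200/200/100) at 0.05, the 2-df figures are 49%, 85%, 98% and over 99%, and the pooled figures 14%, 27%, 43% and 61%.

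A significant 2-df test is not yet a false claim about both. If the reader also asks that both point estimates lie above control, simulation gives 38%, 48% and 50% at d = 0.3, 0.4 and 0.5 (160/160/80, alpha 0.05), and 45% at d = 0.5 with alpha 0.05/61. That is still far above 2.5%.

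**The case against.** The strongest reply is that the plan never says there is a single test. The same singular phrase covers Hypothesis 1a, which compares two arms, so it may name a kind of model term rather than one three-arm test. Section VIII.B also speaks of an effect being significant for either hypothesis, which suggests a separate result for each. Two pairwise interactions, both required, would fit the sentence and would be valid. This stands: a reader might infer that the plan commits to an omnibus test, and the documents do not support that. They leave the contrast open. The nested-model likelihood ratio comparison points towards the three-arm test and the looser restatement of 1b allows pooling, but neither settles it. No section writes the rule that both must win.

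A second reply is that the effect sizes at each time point would show up an idle or harmful arm. This stands in part. If MBCT did worse than control, a claim that it was superior would hardly survive the effect-size table, so the inference that a harmful therapy would be declared superior goes too far. A null therapy whose estimate happens to lie above control is a different matter: descriptive effect sizes carry no decision rule, and that is the case worked above.

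A reader might also infer that the primary analysis is compromised. Hypothesis 1b is labelled secondary, and 1a is untouched if it is run as its own CBT-minus-MBCT contrast. Only if one three-arm term served both hypotheses would 1a share the problem, and the documents do not say that it would.

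**Conclusion.** The point holds as a gap between claim and decision rule: the plan states a joint hypothesis and gives no rule that establishes it. Under the two single-test readings that the text permits, a significant result with only one active therapy ranges from 12% (pooled, 0.2 SD) to 99.5% (three-arm, 0.5 SD) at 0.05, and from 0.5% to 89% at 0.05/61. The stricter alpha shrinks the problem, greatly so for the pooled test, but does not remove it for the three-arm test. The percentages rest on the assumed effects, SD 1 slopes and equal attrition; the logic does not. Because 1b is secondary and the remedy is wording, this should be fixed but does not threaten the primary comparison.

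**What to change.** For Hypothesis 1b, replace the interaction sentence in section VIII.B with two named treatment-by-time contrasts, CBT minus Fitbit-only and MBCT minus Fitbit-only, each with an estimate and confidence interval. Conclude that both are superior only if each is significant in favour of therapy; otherwise name the therapy that was. Specify Hypothesis 1a as its own CBT-minus-MBCT contrast. State one alpha for 1b, since VIII.B gives 0.05 for every test while VIII and VIII.D give 0.0008 for secondary analyses.

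No change to design or data collection is needed. The cost is power for the joint claim. With 160/160/80 and equal true effects, each contrast has standard error √(1/160 + 1/80) = 0.137, and the two share the control arm (correlation 2/3):

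| True effect, alpha | Both contrasts | 2-df test | Pooled test |
|---|---|---|---|
| 0.5 SD, 0.05 | 93% | 96% | 98% |
| 0.3 SD, 0.05 | 46% | 57% | 67% |
| 0.5 SD, 0.05/61 | 49% | 64% | 74% |
| 0.3 SD, 0.05/61 | 6% | 11% | 17% |

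The loss is small only at the larger effect with alpha 0.05. The choice of alpha matters more to the joint claim than the choice of rule, which is a further reason to settle it in the text.
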